In this pilot study, we will evaluate the feasibility and acceptability of our protocol to explore the functional post-operative trajectory in a developmentally and neurologically impaired pediatric population. We will evaluate consent rate, protocol delivery and outcome completion, and acceptability. We will also describe common elements of the experience of these children and their families, including information from a functional skills questionnaire, parental descriptions of pre-post abilities, and parental descriptions of their own quality of life. The objectives of our research are:

Primary outcomes

Objective 1: To evaluate the feasibility and acceptability of our study protocol for children and families living with SNI.

To evaluate feasibility we will use the following evaluation points:

1. Consent rate: The overall average consent rate of children/month.
2. Protocol delivery: The percent of on/off protocol children.
3. Outcome completion: The percent of children with complete outcome measures.

To evaluate acceptability, we will conduct end-of-study interviews with caregivers to assess outcomes related to the ease and utility of participating in the study, including our methods of data collection.

Secondary outcomes:

Our secondary aim is to explore patterns of recovery in children with SNI during the peri-operative period. We will assess:

Objective 1: Function in children with SNI, including exploring patterns in specific domains of gain/loss.

Objective 2: Quality of life in children with SNI and their families

Objective 3: Profile of inflammatory biomarkers to compare children's inflammation levels peri-operatively.

HYPOTHESIS

We expect to confirm feasibility and acceptability of conducting peri-operative research in this population, with at least 12 children consented in 1 year and >85% protocol delivery and outcome completion. We anticipate to be able to measure PoFD, quality of life for children and caregivers, and inflammatory biomarkers.

METHODOLOGY

Study Design

This study will use an observational, pre-post intervention design to evaluate our methods of documenting the post-operative functional trajectory and quality of life in children with SNI and their families during the peri-operative period. We will explore the functional abilities and quality of life of children with SNI and their parent/caregivers pre- and post- major orthopaedic surgery, and we will undertake measurements of inflammatory biomarkers

Study Population

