Our study population will include 12 children with SNI and their parent/caregiver planning to undergo major orthopaedic surgery at the BC Children's Hospital Orthopaedic Clinics. One parent/caregiver may participate per child participant (the same parent/caregiver throughout the study).

Our study defines children with SNI as those with significant neurological disorders and evidence of developmental delay across all domains of daily function, who rely on assistive devices/technology for daily activities and well-being, such as mobility aids or feeding devices⁸ To accurately assess the functional status of our participants for screening pre-operatively, we will use the Gross Motor Function Classification System (GMFCS)³⁰ and the Communication Function Classification System (CFCS)³¹ during participant screening.

The GMFCS is a valid and reliable five-level standardized tool used to classify children and youth with SNI based on their level of movement ability^{30,32-34}. For this study, we will include children classified at Levels II to V. Children in Level II may have difficulty balancing on uneven terrain, inclines, in crowded or confined areas and may require physical assistance or mobility device for walking over long distances. Children in Level III will walk with hand-held mobility devices and use wheeled mobility when traveling long distances. Children in Level IV have severe limitations in their walking ability, including with assistance, and rely on a wheelchair most of the time. Children in Level V have profound physical impairments that impact their head and trunk postural control; they are unable to sit, stand, or walk independently and voluntarily.

The CFCS is a valid and reliable five-level tool used to classify how individuals communicate with familiar and unfamiliar partners³¹. For our study, we will include children at Levels II to V. Children at level II alternates between being sender and receiver but may converse slower. Children at level III will typically communicate effectively with familiar communication partners, but not with unfamiliar partners. Children at Level IV are inconsistent in their ability to communicate with familiar communication partners. Children at Level V are rarely able to communicate effectively, including with familiar people, and often require alternative communication methods to interact.

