We aim to recruit 12 study participants and 5 control participants for this pilot study, which will be useful to 1) test the feasibility and acceptability of our methods and tools for later use on a larger scale, and 2) allow us to describe patterns in preliminary data to identify early associations that may guide the methodology of a larger study. A sample size of 12 study participants and 5 control participants is likely feasible, as the Orthopedic Clinic sees an average of 50 children for hip/spine surgery each year.

STUDY PROCEDURES

The study will include a total of six timed assessments (**Figure 1**). This includes three primary study assessments to collect functional survey and biomarker data: 1) at baseline (within three months of surgery), 2) 6 weeks post-operatively, and 3) 6 months post-operatively. Additionally, we will conduct three biomarker-specific collections during the time of surgery immediately prior to the initiation of the procedure, 12-24 hours post-operatively, and 1-2 weeks post-operatively, based on the physiology of the sequence of the innate and adaptive immune response systems. Most study assessments will be timed at standard of care visits at the BC Children's Hospital. Each primary study visit will take approximately 25-30 minutes. Total time of participation will be 1.5 – 2 hours. Measures will be taken congruently with standard clinical care data collection where possible to reduce participation burden. Some participants may be recruited exclusively for functional/quality of life data collection while the team awaits approvals for blood collection and storage, to allow for an increased sample size.

Baseline Data Collection

Study participants who have consented will undergo a total of 3 primary study visits and 6 biomarker collections (**Figure 1**). At Study assessment #1, demographic information for the child (including variables such as age, sex, race/ethnicity, primary diagnosis, GMFCS/CFCS/MACS score) and demographic information of the parent/caregiver (age, sex, relationship to child, employment status, household income, race/ethnicity, distance from home to primary medical facility) will be collected. Outcome measures (see below) will also be collected. Baseline data collection aims to capture the initial status of participants before any surgical intervention, providing a reference point for post-operative comparisons.

Outcome Measures

The follow study procedures correspond to our primary aims:

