To assess feasibility, we will evaluate three primary feasibility outcomes at the time of data analysis. We will calculate consent rate, which is the overall average consent rate of children/month; protocol delivery, which is the percent of on/off protocol children; and outcome completion, the percent of children with complete outcome measures.

To assess acceptability, anytime after the 6-week timepoint, we will conduct semi-structured interviews with families to assess their experience in participating in this study. We will also ask families if there were any domains that were not included in our standardized functional/quality of life questionnaire and questions. Parents may select from pre-identified domains as prompts (including pain, energy, and sleep), and may also provide additional insight through open-ended conversation. Interviews will be recorded, transcribed, and analyzed using thematic analysis.

The follow study procedures correspond to our secondary aims:

Our primary tool for this study to measure our outcomes of function and quality of life will be the Caregivers Priorities and Child Health Index of Life with Disabilities (CPCHILD) Questionnaire³⁵, which has

been proved to be both valid and reliable^{35,36}. The CPCHILD Questionnaire is used to assess the effectiveness of interventions aimed at improving and preserving outcomes for children aged 5-18 years old with severe disabilities, based on caregivers' perspectives. This questionnaire includes 37 items collected from the parent/caregiver measured across six domains: Personal Care/Activities of Daily Living; Positioning, Transferring, and Mobility; Comfort and Emotions; Communication and Social Interaction; Health; Child's Overall Quality of Life; with additional sections for Importance of Items to Child's Quality of Life, Facts about the Child, and Facts about the Caregiver. From responses, standardized scores can be retrieved on a scale of 0 to 100 for each domain, as well as a total score, and we will be examining comparisons at the item-level pre/post-operatively.

Parents/caregivers will also be asked to answer two supplemental questions to provide further insight into 1) other areas of function that were not described by CPCHILD and 2) the quality of life of caregivers.

Blood collection of study participants

To collect information regarding the peri-operative inflammatory profile, we will collect blood samples from study participants at all study time points:

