Further, our Research Nurse will extract medication, surgery, and anesthetic-specific data (e.g. pain management drugs [anti-inflammatory, steroids, and immune-suppressants], surgery duration, anaesthesia-specific exposure) pre- and post-operatively from participants' electronic medical records for our team to better contextualize PoFD and inflammatory response.

Timeline

Measures will be taken at baseline (within three months of surgery), at the time of operation, 12-24 hours following operation, 1-2 weeks following operation, 6 weeks post-operatively and 6 months post-operatively as per the schedule below. Study visits will be timed congruently with standard clinical care visits or pre-operative/post-operative clinic visits.

[figure not shown]

Figure 1. Study timeline for study participants

DATA ANALYSIS

Data analysis will focus primarily on evaluating the feasibility and acceptability of the study protocol. Baseline descriptive data will be presented as median and interquartile ranges, and categorical data by percentages. Primary feasibility outcomes (consent rate, protocol delivery, and outcome completion rates) will be described as percentages. Acceptability data will be analyzed from semi-structured interviews. Qualitative data from interviews with families will be analyzed using thematic analysis to identify common themes and insights regarding their experiences with the study protocol.

For secondary outcomes related to improvement and/or decline, we will describe patterns in 1) child's function, 2) quality of life of child and caregiver, and 3) inflammatory profile pre- and post-operatively. Given our small sample size, we cannot statistically confirm correlations of PoFD and inflammatory biomarkers, though we may detect patterns in specific markers.

In our analysis (all outcome measures), we hope to stratify our results by sub-category of GMFCS 5, as has been done previously. The sub-categories are presence of a gastrostomy tube, a tracheostomy,

history of seizures, and nonverbal status. Patients with 0 impairments will be classified as GMFCS level 5.0, patients with 1 impairment as level 5.1, patient with 2 impairments as level 5.2, and patients with 3 or more impairments as level 5.3. This stratification will allow us to examine participants' response to surgery based on an indicator of severity of their neurological impairment.

Blood collection

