
With respect to statistical analysis of our control group, our primary analysis will involve a group comparison at each timepoint to assess whether, and to what extent, any biomarkers are altered (increased or decreased) in children with SNI compared to our controls. Given the large biomarker panel (approximately 120 biomarkers), data visualization using volcano plots will be employed. Multiple comparison adjustments will be applied using the false discovery rate (FDR) correction method (Benjamini-Hochberg). Biomarker significance will be determined based on effect size thresholds, specifically log2(fold change), with a significance level set at 5% (Type I error). Additionally, associations between biomarkers and study variables (e.g., age, sex) will be explored using Wilcoxon rank-sum tests.

Outcomes

The following outcomes will be utilized to deem our study feasible and acceptable:

Feasibility:

1. Consent rate: An average consent rate of 2-3 children/month
2. Protocol delivery: The protocol can be implemented with >85% protocol delivery.
3. Outcome completion: >85% of outcomes will be complete and measured as scheduled.

Acceptability:

4. General positive report on participation based on semi-structured interview

Secondary outcomes; we will explore pre- and post-operative data to describe patterns in:

1. Function of the child, as scored on the CPCHILD;
2. Quality of life of caregiver, as described by supplemental question;
3. Inflammatory profile of child

DATA STORAGE

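### Outcome completion is defined per child without a timing condition, but judged feasible per outcome with one, under the same >85% threshold

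*Protocol*

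**What the plan says.** The protocol describes outcome completion in five places.

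- **Study Objectives, Primary outcomes, item 3:** "Outcome completion: The percent of children with complete outcome measures". The unit is the child and timing is not mentioned.
- **Hypothesis:** the expectation is ">85% protocol delivery and outcome completion". This puts the threshold on the term just defined, again without timing.
- **Outcome Measures, primary aims:** "outcome completion, the percent of children with complete outcome measures". The per-child definition is repeated.
- **Data Analysis:** "Primary feasibility outcomes (consent rate, protocol delivery, and outcome completion rates) will be described as percentages". No denominator is given.
- **Outcomes, Feasibility, item 3:** ">85% of outcomes will be complete and measured as scheduled". The unit is now the outcome, and being on schedule is added as a requirement.

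The last list is introduced by the sentence "The following outcomes will be utilized to deem our study feasible and acceptable", so it carries the verdict.

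**The concern.** One label and one threshold cover two different quantities. A per-child rate counts a child as a failure if any measure is missing. A per-outcome rate counts only the missing measure itself. Separately, the timing condition turns a late but complete measure into a failure under one statement and leaves it a success under the other.

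Feasibility is the primary objective of this pilot, and its results are meant to help finalise the protocol of a larger study. If the two statements give different answers, whoever writes the report can choose between them after seeing the data, and either choice can be supported from the protocol.

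**Working it through.** The >85% threshold is a chosen criterion with no derivation in the protocol, so there is no figure to reproduce. The check is whether the two statements can disagree on the same data.

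**Inputs**
- Children: 12. Study Population states "Our study population will include 12 children with SNI".
- Assessments per child: 3. Study Procedures lists "three primary study assessments to collect functional survey and biomarker data".
- Assumption: one primary assessment counts as one outcome, giving 12 × 3 = 36. The protocol does not say what is counted.

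**Smallest count that exceeds 85%**
- Per child: 0.85 × 12 = 10.2, so at least 11 of 12 (91.7%); 10/12 = 83.3% fails.
- Per outcome: 0.85 × 36 = 30.6, so at least 31 of 36 (86.1%); 30/36 = 83.3% fails.

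**Unit alone.** Suppose *k* children each miss one assessment and all others are done on time. The per-child rate is (12 − *k*)/12 and the per-outcome rate is (36 − *k*)/36.

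| *k* | Per child | Per outcome | Verdicts |
|---|---|---|---|
| 1 | 11/12 = 91.7% | 35/36 = 97.2% | both pass |
| 2 | 10/12 = 83.3% | 34/36 = 94.4% | split |
| 3 | 9/12 = 75.0% | 33/36 = 91.7% | split |
| 4 | 8/12 = 66.7% | 32/36 = 88.9% | split |
| 5 | 7/12 = 58.3% | 31/36 = 86.1% | split |
| 6 | 6/12 = 50.0% | 30/36 = 83.3% | both fail |

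**Timing alone.** All 36 assessments are done but 6 are late. Per child without a timing condition: 12/12 = 100% (pass). Per outcome and on schedule: (36 − 6)/36 = 83.3% (fail). The split now runs the other way, so neither statement is simply a stricter form of the other.

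**Other denominators**
- Six blood collections per child as the unit: 12 × 6 = 72, and at least 62 are needed (62/72 = 86.1%). Two children missing one sample each give 10/12 = 83.3% against 70/72 = 97.2%.
- Controls included: 12 + 5 = 17 children. Two incomplete children give 15/17 = 88.2%, which passes. Three give 14/17 = 82.4%, which fails. Counting the controls' three blood draws as outcomes, the per-outcome rate is then (36 + 15 − 3)/51 = 94.1%, which passes.
- More children: the two-child example holds up to 13 children (11/13 = 84.6%) and stops at 14 (12/14 = 85.7%), but the mechanism remains. At 24 children, four missing one each give 20/24 = 83.3% against 68/72 = 94.4%.

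**How likely a split is, under assumed rates.** Let each assessment be completed with probability *c* and be on time with probability *t*, all independent. The per-child rule passes with probability P(X ≥ 11), X ~ Bin(12, *c*³). The per-outcome rule passes with probability P(Y ≥ 31), Y ~ Bin(36, *ct*).
- *c* = 0.95, *t* = 1.00: 0.47 per child, 0.99 per outcome.
- *c* = 0.98, *t* = 0.85: 0.85 per child, 0.43 per outcome.

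These rates are illustrative; the protocol gives none.

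**The case against.** The strongest reply is that the passages have different roles. The objectives name what will be evaluated, the Hypothesis states an expectation, and only the feasibility list decides. On that reading the list governs. It is a reasonable reading, but no text says so, and the Hypothesis sets the same threshold on the per-child term.

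A second reply is that item 3 is loose shorthand: its label has already been defined per child, and being complete may be taken to include being on time because a schedule exists. If that is granted for timing, the unit still differs, and the unit alone splits the verdict.

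Third, the size depends on how the examples are built. This is partly right. The 36 is an assumption. The missing-data example needs the remaining assessments to be on time. Lateness has no stated window around 6 weeks or 6 months. Baseline can be taken up to the day of surgery and so can hardly be late, which makes six late assessments 6 of the 24 postoperative ones, or 25%, a rate the documents do not support. These points limit what can be said about likelihood. They do not remove the conflict, which also appears with the other denominators.

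Finally, this is a small descriptive pilot, and both rates can be computed from the same data and reported together. That is true and limits the harm, but reporting both does not say which one decides.

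**Conclusion.** The concern holds with high confidence and should be fixed. The protocol gives two non-equivalent definitions of a primary feasibility outcome under one threshold. This is not detail left to an SAP, because an SAP that adopted either definition would depart from the other.

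With 12 children and three assessments each, the verdict splits whenever two to five children miss one assessment apiece and the rest are on time. It splits in the opposite direction if all are complete but six are late. The exact counts rest on treating one primary assessment as one outcome and on counting only the 12 study children; the existence of the conflict does not. One of three primary feasibility verdicts is affected, with no consequence for safety or treatment.

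**What to change.** Before data are seen, use the same unit and the same timing condition in Study Objectives, Outcome Measures and the feasibility list under Outcomes.

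- **Unit.** The simplest alignment is to restate feasibility item 3 per child, as both definitions already do: more than 85% of children complete, which is at least 11 of 12. The per-outcome rate can be reported as description.
- **Timing.** Either remove the on-schedule condition from item 3 and report the on-schedule percentage descriptively, or carry the condition into both definitions. If it stays, the sponsor should state what counts as on schedule at 6 weeks and 6 months.
- **Blood samples (secondary).** In the same sentence, say whether a child without blood samples can count as complete, since sampling is optional and some children may be recruited for questionnaires only.

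The cost is aligned wording in three places and no new data. The per-child figure may look less favourable than the per-outcome one, and a per-child rule that keeps the timing condition would be stricter still.
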